6.4. Multiple Imputation – Categorical Sensitivity Analysis

The primary multiple imputation method will treat IGA/PGA as continuous when used as covariates for the logistic regression model. As a sensitivity analysis, the multiple imputation process for IGA/PGA will be repeated treating those predictors as categorical.

First, the pattern of missingness in the data will be evaluated. If the data is not monotone missing, the MCMC method will be used to make it monotone missing. The single chain method will be used, with 200 burn-in iterations and 100 iterations between imputations. Fifty imputations will be created. If all subjects have the same baseline IGA/PGA value, the baseline visit will not be included in the model. The seed number will be 18251. IGA and PGA scores generated as a result of the MCMC method will be rounded prior to the next step; scores will be re-imputed if, after rounding, they are lower than 0 or higher than 4.

Due to the categorical nature of the data, and the rarity of some values of IGA/PGA, there is the potential for convergence issues when using logistic regression with categorical covariates. If this is the case, each week will be imputed sequentially and predictor weeks that cause convergence issues (and thus can't be used as valid predictors) will be dropped.

The model will be chosen by first checking if the inclusion of any covariates causes convergence issues. If so, predictor weeks will be removed from the model and the model rerun until any convergence issues are solved. Earlier weeks will be dropped from the model before later weeks, and combinations of weeks will only be dropped if the removal of only one week does not cause the model to converge. Thus, weeks will be dropped in the following order:

1. Week 1
2. Week 2
3. Week 4
4. Week 8
5. Weeks 1 and 2

6. Weeks 1 and 4
7. Weeks 2 and 4
8. Weeks 1 and 8
9. Weeks 2 and 8
10. Weeks 4 and 8
11. Weeks 1, 2, and 4
12. Weeks 1, 2, and 8
13. Weeks 2, 4, and 8

After each removal, the model will be rerun. The first model that converges will be kept, and the process will restart with the next week until Week 12 is imputed. The final chosen models will be run with seed number 18251. Below is an example of the SAS syntax for the MCMC and logistic MI procedures treating predictor weeks as categorical, with no weeks removed:

```
proc mi data=transI seed=18251 out=mcmcI(rename=_imputation_=imp) nimpute=50
minimum=0 maximum=4 round=1;
mcmc impute=monotone chain=single nbiter=200 niter=100;
var trt01pn baseline week_1 week_2 week_4 week_8 week_12;
run;
```

```
proc mi data=mcmcI seed=18251 out=miI nimpute=1 noprint;
by imp;
class trt01pn baseline week_1 week_2 week_4 week_8 week_12;
var trt01pn baseline week_1 week_2 week_4 week_8 week_12;
monotone logistic(week_1=trt01pn baseline);
monotone logistic(week_2=trt01pn baseline week_1);
monotone logistic(week_4=trt01pn baseline week_1 week_2);
monotone logistic(week_8=trt01pn baseline week_1 week_2 week_4);
monotone logistic(week_12=trt01pn baseline week_1 week_2 week_4 week_8);
run;
```

6.5. Analysis of Percent Change in Lesion Count

The percent change in lesion count will be analyzed using a CMH test using ridit scoring. The resulting test statistics for the row-mean scores difference from the CMH analysis will be combined using the procedure by Rubin (1987) and Li et al. (1991) to produce a pooled CMH statistic and p-value.

6.6. Missing as Failure Analysis of Lesion Counts

The missing-as-failure analysis will be used for lesion counts to impute missing lesion count change from baseline at week 12.

For missing facial lesion count data, the median change from baseline in lesion counts from among all observed IGA failures at Week 12 will be substituted. For missing truncal lesion count data, the median change from baseline in lesion counts from among all observed PGA failures at Week 12 will be used.

In both cases the median will be calculated separately for each treatment group, using actual treatment, and the imputation will use the median that corresponds to the treatment group of the subject being imputed.

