5.1 Intention to Treat (ITT) Population

The ITT population is defined as any subjects who are randomized. Data from subjects included in the ITT population will be analyzed according to the treatment as randomized.

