6 SAMPLE SIZE CONSIDERATION

The assumptions used to power this study are based on the phase 2 study (SPR18223). Success rates based on IGA are assumed 23% (CD5789) and 15% (Vehicle). For a 90% power to detect a significant difference versus vehicle using a two-sided test at a type I error of 0.05, 504 subjects per arm are needed for analysis. To compensate for drop-outs and non-evaluable subjects (estimated at 16%), a total of 1200 subjects are to be randomized (600 per arm).

Based on the results from stratum 1 in the phase 2 study (SPR18223), the mean difference between the active and vehicle is estimated at 3 inflammatory lesions and 6 non-inflammatory lesions. Standard deviation of changes in lesion counts, based on phase 2 and on large phase 3 trials from other projects are estimated at 12 for inflammatory lesions and 20 for non-inflammatory lesions. Using these as assumptions and a sample of 504 evaluable subjects per arm, power is above 95% for both lesion types.

The assumptions for truncal acne being the same as for facial acne in terms of efficacy, therefore it is estimated that the power for truncal acne is adequate.

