Changes from baseline in facial lesion counts will be analyzed separately by type (inflammatory and non-inflammatory) using an ANCOVA (Analysis of Covariance) model including baseline count, analysis center, and treatment as factors. The primary analysis will be performed using the ITT population using the primary imputation method for missing values.

The p-value for the treatment comparison, estimate of the LSMEANS treatment difference (CD5789 50 µg/g – Vehicle), and the 95% confidence interval of the LSMEANS difference will be generated from the ANCOVA model.

The treatment-by-analysis centers and the treatment-by-baseline lesion counts interactions for Change in Lesions Counts will be assessed separately by the interaction term at Week 12 at alpha level of 0.10. The consistency of the treatment effect across analysis centers will be evaluated using descriptive statistics and using graphical methods. The consistency of the treatment effect by baseline lesion counts will be evaluated using graphical methods.

In addition, change in Lesions Counts will be summarized descriptively at each visit.

Sensitivity analyses

The above primary efficacy analysis will be repeated using the PP population using the primary multiple imputation method for missing values.

To assess the robustness of the primary efficacy result, the following sensitivity analyses will be conducted for each of the 3 co-primary efficacy endpoints (see Section 4.1) using the ITT population:

- a. The same imputation method above will be repeated based on the Pattern-Mixture Model⁽²⁾ under the missing not at random (MNAR) assumption, by using the profiles from vehicle subjects with observed data to impute missing data.
- b. LOCF (Last observation carry forward) approach
- c. Subjects with missing IGA data at Week 12 will be considered as ‘failures’ for IGA success rate; and subjects with missing lesion counts data at Week 12 will be assigned the median change of lesion count data from subjects who are ‘failures’ of IGA success within the same treatment group.

7.4.1.2 *Analysis of the Secondary Efficacy Endpoint*

The same statistical methods planned for the 3 co-primary efficacy endpoints will be used for the analyses of the 3 co-secondary efficacy endpoints using the ITTT population, with Multiple Imputation (MI) as primary imputation method for missing values (see Section 7.4.2.2).

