7.4.2.2 Handling of dropouts or missing data

The primary method of imputation for missing data will be MI (Multiple Imputation) using the Missing At Random (MAR) assumption.

For the primary MAR based multiple imputation, the MI procedure of the SAS system will be used to generate sets of data with missing values imputed from observed data. It is expected that the pattern of missing data will be monotonic, with slight deviations being corrected by the Markov Chain Monte Carlo (MCMC) method of the MI procedure.

Linear regression will be employed to model the missing lesion count data and a logistic regression model will be used for the ordinal IGA/PGA scores, with the following covariates included in the imputation model: treatment and non-missing data from earlier timepoints. IGA/PGA success will be calculated from the imputed IGA/PGA scores. The imputed datasets will be analyzed using the methodology described in Section 7.4.1.1 for changes in lesion counts, and IGA/PGA success. The results from the analysis of the multiple imputed datasets will be combined by the MIANALYZE procedure of the SAS system. The seed number to be used will be the protocol number (18251) and the number of imputation is planned to be 5.

For success rate, the final p-value from the CMH test stratified by analysis center on each multiply imputed dataset will be generated using the Schafer, J. L.⁽³⁾ Multiple Imputation Methodology. The final difference of success rate between treatment groups (CD5789 50 µg/g – Vehicle) and the 95% confidence interval of the final difference from each multiply imputed dataset will be generated using the method by Bohdana Ratitch ed. al.⁽⁴⁾.

For changes in lesion counts, the final p-value, treatment difference (CD5789 50 µg/g – Vehicle), and the 95% confidence interval of the treatment difference from the ANCOVA model on each multiply imputed dataset will be generated from the MIANALYZE procedure of SAS.

To assess the robustness of the primary efficacy results, the following sensitivity analyses will be also conducted:

- a. The same imputation method above will be repeated based on the Pattern-Mixture Model under the missing not at random (MNAR) assumption, by using the profiles from vehicle subjects with observed data to impute missing data.

b. LOCF (Last observation carry forward) approach

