c. Subjects with missing IGA/PGA data at Week 12 will be considered as ‘failures’ for IGA/PGA success rate; and subjects with missing lesion counts data at Week 12 will be assigned the median change of lesion counts data from subjects who are ‘failures’ of IGA/PGA success within the same treatment group.

7.4.2.3 *Interim analyses and data monitoring*

No interim analysis is planned for this study.

7.4.2.4 *Multicenter studies*

A small center is defined as the center which randomizes less than 8 subjects. Small centers will be pooled prior to analyses. First, centers will be sorted by country, number of randomized subjects (descending order) and center number (ascending order). Pooling will start with combining the largest of the set of small centers with the smallest center within that country. If there is a further need to combine data (the size of the pooled centers includes less than 8 subjects), the next smallest center will be combined with the next largest of the small centers, until the criterion of a minimum of 8 subjects is met. The process will continue until all pooled centers have a minimum of 8 subjects within the country. Any remaining centers will be pooled with the last pooled center within the country. The pooled centers will be referred to as ‘analysis centers’ in the statistical analyses.

7.4.2.5 *Multiple comparison/multiplicity*

Control of type 1 error, the experiment-wise error rate is controlled at alpha level of 0.05.

No adjustment for multiplicity is required for the primary efficacy endpoint as the statistical significance needs to be met for all 3 co-primary endpoints.

The statistical inferential testing for the secondary primary efficacy endpoint is conditional on the statistical significance of the primary efficacy endpoint, and all 3 co-secondary efficacy endpoints are required to reach statistical significance for the secondary efficacy endpoint to be statistically significant.

Therefore, no adjustment for multiplicity is required in this study.

7.4.2.6 *Use of an efficacy subset of patients*

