6.3. Multiple Imputation – Missing Not at Random

As a sensitivity analysis, the multiple imputation process will be repeated assuming that the data is missing not at random. This process will be the same as the one described for the Missing at Random analysis, but with the assumptions changed. The Missing Not at Random dataset will use data collected from vehicle subjects to impute missing observations.

Below is an example of the SAS syntax for the logistic MI for IGA/PGA for the missing not at random assumption:

```
proc mi data=transI seed=18251 out=miI1 nimpute=50 noprint;
class trt01pn baseline week_1;
var baseline week_1;
monotone logistic(week_1=baseline);
mnar model(week_1 / modelobs=(trt01pn="2"));
run;

proc mi data=miI1 seed=18251 out=miI2 nimpute=1 noprint;
by _IMPUTATION_;
class trt01pn baseline week_2;
var trt01pn baseline week_1 week_2;
monotone logistic(week_2=baseline week_1);
mnar model(week_2 / modelobs=(trt01pn="2"));
run;

proc mi data=miI2 seed=18251 out=miI3 nimpute=1 noprint;
by _IMPUTATION_;
class trt01pn baseline week_4;
var trt01pn baseline week_1 week_2 week_4;
monotone logistic(week_4=baseline week_1 week_2);
mnar model(week_4 / modelobs=(trt01pn="2"));
run;

proc mi data=miI3 seed=18251 out=miI4 nimpute=1 noprint;
by _IMPUTATION_;
class trt01pn baseline week_8;
var trt01pn baseline week_1 week_2 week_4 week_8;
monotone logistic(week_8=baseline week_1 week_2 week_4);
mnar model(week_8 / modelobs=(trt01pn="2"));
run;

proc mi data=miI4 seed=18251 out=miI(rename=(_imputation_=imp)) nimpute=1
noprint;
by _IMPUTATION_;
class trt01pn baseline week_12;
var trt01pn baseline week_1 week_2 week_4 week_8 week_12;
monotone logistic(week_12=baseline week_1 week_2 week_4 week_8);
mnar model(week_12 / modelobs=(trt01pn="2"));
run;
```

Below is an example of the SAS syntax for the MCMC and linear MI procedures for lesion counts for the missing not at random assumption:

```
proc mi data=transI seed=18251 out=mcmcI(rename=_imputation_=imp) nimpute=50
minimum=0 noprint;
mcmc impute=monotone chain=single nbiter=200 niter=100;
var baseline week_1 week_2 week_4 week_8 week_12;
run;

proc mi data=mcmcI seed=18251 out=miI nimpute=1 minimum=. 0 0 0 0 0 0
noprint;
by imp;
class trt01pn;
var baseline week_1 week_2 week_4 week_8 week_12;
monotone reg(week_12=baseline week_1 week_2 week_4 week_8);
mnar model(week_1 / modelobs=(trt01pn="2"));
mnar model(week_2 / modelobs=(trt01pn="2"));
mnar model(week_4 / modelobs=(trt01pn="2"));

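### The missing-as-failure check of lesion counts fills gaps with one own-arm median and treats it as observed, so its standard error is too small

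*SAP*

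**What the plan says.** SAP 7.4.1.1, sensitivity analysis (c), states for the face that "subjects with missing lesion counts data at Week 12 will be assigned the median change of lesion count data from subjects who are" IGA failures in the same treatment group. SAP 7.4.2.2(c) repeats the rule for face and trunk: "subjects with missing lesion counts data at Week 12 will be assigned the median change of lesion counts data from subjects who are" failures on IGA or PGA. Addendum 6.6 gives the operational form: for the face, "the median change from baseline in lesion counts from among all observed IGA failures at Week 12 will be substituted", and for the trunk the corresponding median among PGA failures. It adds that "the median will be calculated separately for each treatment group, using actual treatment".

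Table 1 of the SAP marks this approach as supportive. It assigns it the same methods as the primary analysis (CMH for success rates, ANCOVA for lesion counts) in the ITT population, or the ITTT population for the trunk. Pooling across imputed datasets is specified in SAP 7.4.2.2 and in Addendum 6.2, 6.3 and 6.5, for the multiple-imputation analyses only. Nothing in these sections adjusts the variance after the single-median substitution.

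The primary method is different: "The primary method of imputation for missing data will be MI (Multiple Imputation) using the Missing At Random (MAR) assumption".

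**The concern.** A missing value replaced by a constant enters the ANCOVA as a full observation with almost no residual of its own. The model counts the extra subjects, the residual variance falls, and the standard error shrinks as though information had been gained. A check that exists to test robustness can then look firmer than the data allow. It covers four endpoints: two facial co-primary and two truncal co-secondary lesion counts.

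Two smaller points come with it.

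- The label suggests that dropouts are penalised. Vehicle dropouts also receive a failure's value, taken from their own arm, so most of the treatment difference survives among dropouts.
- The median is selected by treatment received, whereas SAP 5.1 states that "Data from subjects included in the ITT population will be analyzed according to the treatment as randomized". This matters only for a subject who both received the wrong treatment and lacks a Week 12 count.

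**Working it through.** **Inputs from SAP section 6.** 600 randomized and 504 evaluable per arm; a 16% allowance for loss; SD of change 12 (inflammatory) and 20 (non-inflammatory); effects of 3 and 6 lesions; IGA success 23% against 15%; two-sided 5% level.

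**The plan's own figures reproduce.** Two proportions, 23% v 15%, 90% power, no continuity correction: 504 per arm. 504/0.84 = 600. Power at 504 per arm is 97.8% for 3/12 and 99.7% for 6/20, so the statement of power above 95% is right. The plan gives no standard error (SE) for the missing-as-failure analysis.

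**Assumption.** Let m be the share of Week 12 counts missing. The SAP gives no such figure. The 16% covers drop-outs and non-evaluable subjects together, and SAP 7.7 counts any visit after day 70 as Week 12, so the true m may be lower.

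**Algebra, SD 12, m = 0.16, baseline ignored.**

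- Observed subjects only: 12 × √(2/504) = 0.756.
- All 600 per arm truly observed: 12 × √(2/600) = 0.693.
- Reported after filling with a constant: 12 × √0.84 × √(2/600) = 0.635.

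The filled-in analysis claims more precision than complete data would give, although 96 subjects per arm have no value. The ratio of the reported to the observed-only SE is 1 − m = 0.84. For SD 20 the figures are 1.058 against 1.260, the same ratio.

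**Simulation against the actual sampling SE.** No true effect, 600 per arm, SD 12, ANCOVA on treatment and baseline (centre omitted), IGA success 19% in both arms, missing completely at random, 4,000 trials per setting. The settings cross baseline-change correlation 0 or 0.5, correlation of change with the latent IGA response 0.3 or 0.6, and normal or skewed errors. The correlations and skewness are assumptions.

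| Share missing | Reported SE / actual SE | Rejection at nominal 5% |
|---|---|---|
| 5% | 0.944-0.971 | 5.5-6.5% |
| 10% | 0.895-0.934 | 6.7-8.3% |
| 16% | 0.824-0.881 | 8.1-10.6% |

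When poor responders drop out more often (logit slope 0.5 per SD of change, 3,000 trials), rejection is 7.7-8.1% with the intercept set for 10% missing and 10.1-10.4% when set for 16%.

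A separate simulation with the planned effects present and other correlations (8,000 trials per setting) puts the shortfall at 12.3-16.7% at 16% missing; nominal 95% intervals miss the estimator's own mean 8.6-10.4% of the time. A further null run gives ratios of 0.82-0.83 and rejection of 10.7-11.3% at 16% missing. These agree with the table to within Monte Carlo error and differences in settings.

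**What this does to a p-value.** A reported z of 1.96 corresponds to a correct z between 1.96 × 0.824 = 1.615 and 1.96 × 0.881 = 1.727, that is p = 0.106 to 0.084. At 16% missing, a result whose correct p lies between 0.05 and that bound is shown as significant.

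**How much penalty the check applies.** With the planned effects and 16% missing, active dropouts receive a value 1.4-3.7 inflammatory lesions worse than the observed active mean. They still keep 2.1-2.6 of 3 inflammatory and 4.6-5.4 of 6 non-inflammatory lesions over vehicle dropouts. The overall estimate is then about:

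- inflammatory: 0.84 × 3 + 0.16 × (2.1 to 2.6) = 2.86 to 2.94;
- non-inflammatory: 0.84 × 6 + 0.16 × (4.6 to 5.4) = 5.78 to 5.90.

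That is a fall of roughly 2-5%. The simulated means are close to this: 2.88-2.97 and 5.80-5.95 in one set, 2.82-3.01 and 5.76-5.81 in the other.

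**The case against.** The strongest reply concerns consequence. Success is declared on the multiple-imputation analyses alone, and this check is read mainly after they have succeeded. If the planned effects are true and 16% of counts are missing, the understated SE turns a correctly non-significant result into a significant one in only about 1.1% of trials (inflammatory) and 0.3% (non-inflammatory). Among trials whose observed-data test is already significant, the figures are 0.6% and 0.2%. At 5% missing the error is close to negligible. An own-arm failure value is also a legitimate scenario, and a vehicle-based penalty is planned elsewhere: "The Missing Not at Random dataset will use data collected from vehicle subjects to impute missing observations". Labelling the p-value descriptive might therefore be enough.

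Most of this stands as a limit on importance. It does not remove the fault. Robustness checks matter most when the effect is smaller than planned, and with no true effect the share among already significant trials rises to about 18% at 16% missing. A descriptive label would leave the confidence interval too narrow. The lack of penalty is a limit on what the check can show, not an error in itself. The treatment-received point is minor, but its conflict with SAP 5.1 is real.

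**Conclusion.** The concern holds. As written, the analysis understates its standard error at every missing share above zero: by about 12-18% at 16% missing, 7-11% at 10% and 3-6% at 5%. A nominal 5% test then rejects a true null in roughly 8-11%, 7-8% and 5.5-6.5% of trials respectively.

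The direction follows from arithmetic. The size rests on the assumed missing share, correlations and missingness mechanism, and on leaving centre out of the simulations. That the filled-in values are treated as observed is inferred from the named ANCOVA and the absence of any correction.

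The fault is confined to supportive lesion-count analyses on face and trunk. The primary analysis, the trial's 5% error rate and the missing-as-failure success rates are unaffected. It should be corrected, but it does not threaten the trial's main conclusion.

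**What to change.** Replace the single median in SAP 7.4.1.1(c), 7.4.2.2(c) and Addendum 6.6 with wording such as:

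> Each missing Week 12 change will be imputed 50 times by a random draw from a bootstrap sample of the observed Week 12 changes of IGA (trunk: PGA) failures in the subject's randomized arm; the ANCOVA will be run on each dataset and the results combined with MIANALYZE.

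This keeps the intended scenario and reuses the number of imputations and the pooling step already in Addendum 6.2. In three null settings at 16% missing (2,000 trials each) it gave rejection of 4.5%, 4.6% and 5.1%, with reported/actual SE of 0.98-1.03. Its SE for inflammatory lesions, 0.755, matches the 0.756 expected from 504 observed per arm.

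If a penalty against active treatment is also wanted here, use one common constant, the vehicle-arm failure median, for both arms. A common constant cancels from the treatment difference, so the sampling SE is 0.84 × 0.756 = 0.635, equal to the reported SE; simulated rejection was 4.6-5.6%. In either case, define the arm as randomized.

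**Cost.** Addendum wording and a small program change. With own-arm draws the confidence interval is 0.755/0.635 = 1.19 times as wide at 16% missing. With the common constant, a true effect of 3 is estimated at about 2.5 (0.84 × 3 = 2.52; simulated 2.54) and 6 at about 5.1 (0.84 × 6 = 5.04; simulated 5.07). Both costs fall on this supportive analysis only.

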5.2 Intention to Treat on the Trunk (ITTT) Population

The ITTT population is defined as any subjects in the ITT population with moderate truncal acne at the Baseline visit. In practice, this excludes from the ITT population the children between 9 and 11 years old who did not meet inclusion criterion #4 (PGA) or #5 (Truncal lesion counts) at study entry (i.e. who do not have PGA of 3, at least 20 inflammatory lesions on the trunk and at least 20 non-inflammatory lesions on the trunk).

Subjects in the ITTT population will be analyzed according to the treatment as randomized.

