5.3 Safety (SAF) Population

The SAF population is defined as comprising the ITT population subjects who applied/were administered the study medication at least once.

The SAF population is used for all safety analyses, except for the local tolerability on the trunk.

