5.5 Per Protocol Population

The PP population is defined as comprising the ITT subjects who have no major protocol deviations. The primary efficacy analyses (on the face) will be repeated based on the PP Population to confirm the results.

Potential major protocol deviations may include but are not limited to:

1. Entrance Criterion Deviations:
 - a. Out of range baseline lesion counts
 - b. Out of range baseline IGA grade
 - c. Inclusion/exclusion criterion violation
2. Non-Compliance:
 - a. Subjects who have dosing deviations more than 30% of the planned 84 doses
 - b. Subjects who miss doses for 5 or more consecutive days just prior to the last visit
3. Prohibited Medications: Subjects who have taken interfering concomitant therapies during treatment
4. Administrative error:
 - a. Accidental unblinding
 - b. Medication dispensing errors
 - c. Lesion counts and IGA/PGA performed by a non-approved evaluator

The final list of major protocol deviation criteria and subjects who have any major protocol deviations will be documented in the blind review memo before database lock.

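### The missing-as-failure lesion-count medians are formed by actual treatment, although the ITT and ITTT analyses they feed are run as randomized

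*SAP*

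**What the plan says.** Addendum 6.6 fills a missing Week 12 change in lesion count with the median change among observed failures: IGA failures for the face, PGA failures for the trunk. It then sets the grouping: "In both cases the median will be calculated separately for each treatment group, using actual treatment". The same sentence goes on to assignment: "the imputation will use the median that corresponds to the treatment group of the subject being imputed". This second clause does not repeat the word actual.

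Table 1 in SAP 7.4.1.1 runs the missing-as-failure approach on ITT for the co-primary endpoints and on ITTT for the co-secondary endpoints. SAP 5.1 says: "The ITT population is defined as any subjects who are randomized", and "Data from subjects included in the ITT population will be analyzed according to the treatment as randomized". SAP 5.2 says: "Subjects in the ITTT population will be analyzed according to the treatment as randomized".

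Item (c) of the sensitivity analyses in SAP 7.4.1.1, and item (c) in SAP 7.4.2.2, ask only that the median come from the subject's own treatment group, with no mention of treatment received. Addendum section 1 says that the addendum prevails where the two differ.

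Two further passages show that actual and randomized treatment can differ. SAP 5.3 defines the safety population as "the ITT population subjects who applied/were administered the study medication at least once", so ITT may hold subjects with no application. SAP 5.5 lists "Medication dispensing errors" among the potential major deviations. These can remove a subject from the per-protocol population but not from ITT.

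**The concern.** An analysis run as randomized takes its imputed values from groups formed on a different basis, and neither document gives a reason. The main SAP's neutral wording, read with 5.1 and 5.2, points to the randomized group. The addendum replaces it with actual treatment.

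The missing-as-failure analysis is meant to give every subject with a missing Week 12 assessment an unfavourable result. It is a pre-specified robustness check for two co-primary and two co-secondary lesion-count endpoints. If the rule mixes arms, or defines no value for some ITT subjects, it does not fully do that. Two programmers could also code the sentence differently, and a choice made after unblinding would be post hoc.

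**Working it through.** **1. The plan's own figures.** SAP section 6 assumes success rates of 23% and 15%, 90% power and a two-sided 0.05 test. The pooled-variance formula without continuity correction is

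n = [1.960 × √(2 × 0.19 × 0.81) + 1.282 × √(0.23 × 0.77 + 0.15 × 0.85)]² / 0.08² = 503.3, so 504 per arm.

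504 / (1 − 0.16) = 600 per arm. With 504 per arm, lesion-count power is 97.8% (difference 3, SD 12) and 99.7% (difference 6, SD 20). All of these agree with the SAP, and none depends on the imputation rule.

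**2. What each reading of Addendum 6.6 implies**

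| Subject | Assignment by actual treatment | Assignment by randomized treatment |
|---|---|---|
| Mis-dispensed, observed failure | Contributes to the other arm's median | The same, because the medians are still formed by actual treatment |
| Mis-dispensed, Week 12 count missing | Receives the other arm's median | Receives the randomized arm's median |
| Randomized, never dosed, count missing | No value defined | Receives the randomized arm's median |
| Dosed as randomized, count missing | Own arm's median | Own arm's median |

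Only the first row holds on both readings.

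**3. Size of the assignment effect.** The documents give neither the number of mis-dispensed subjects nor the gap between the two failure medians, so both are assumed. Let k subjects in each arm, all missing at Week 12, receive the other arm's median, and let the gap be g. Compared with assignment as randomized, the treatment difference moves toward zero by about 2kg/600. The standard error is SD × √(2/600), which is 12 × 0.0577 = 0.69 (inflammatory) and 20 × 0.0577 = 1.15 (non-inflammatory).

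| Lesion type | g | k per arm | Shift (lesions) | Shift (SE) |
|---|---|---|---|---|
| Inflammatory | 1 | 1 | 0.003 | 0.005 |
| Inflammatory | 3 | 12 | 0.12 | 0.17 |
| Non-inflammatory | 2 | 1 | 0.007 | 0.006 |
| Non-inflammatory | 6 | 12 | 0.24 | 0.21 |

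The largest gaps used, 3 and 6, equal the whole planned treatment differences.

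**4. Size of the effect on the medians themselves.** At the planned rates, the observed failures number about 0.77 × 504 = 388 and 0.85 × 504 = 428. Suppose 12 failures in each arm received the wrong product and responded according to the product received. Each median then differs from its as-randomized version by roughly its swapped fraction times g. At most 16% of subjects are imputed (0.16 × 600 = 96 per arm), so the treatment difference changes by about 0.16 × (12/388 + 12/428) × g = 0.0094g. That is 0.03 lesions for g = 3 and 0.06 for g = 6, or about 0.04 and 0.05 SE. The direction is opposite to step 3, because grouping by product received separates the two medians slightly.

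**5. If never-dosed subjects received no value.** Each 1% never dosed is 12 of 1,200. If 6 to 24 per arm had no value and were left out, inflammatory power would go from 99.1% at 600 per arm to between 99.1% and 98.9%. Non-inflammatory power would stay near 99.9%.

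**The case against.** The strongest reply is that the words about actual treatment govern only how the medians are calculated. The assignment clause speaks of the subject's treatment group, and in ITT and ITTT that is the randomized group. On this reading never-dosed and mis-dispensed subjects all receive their randomized arm's median, and what remains is a slight effect on the donor medians. The reading is possible. It is the less natural one, because the same sentence has just formed the groups by actual treatment. It also leaves the medians on the wrong basis.

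A reader might go further and infer that never-dosed subjects are dropped, that the earliest drop-outs are excluded, or that the co-primary endpoints are therefore assessed on different subjects. The documents do not support these as statements of the plan. No passage excludes never-dosed subjects: Table 1 keeps the analysis on ITT, and the main SAP says that subjects with missing counts are assigned a median. The text is silent on the never-dosed. An early drop-out who applied the product once has an actual treatment and receives a value.

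It is also fair to say that the reach is narrow. This is the lesion-count part of one of four supportive approaches in Table 1. The decision rule, the primary multiple imputation and the IGA/PGA missing-as-failure rule do not use it.

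**Conclusion.** The inconsistency is real. Addendum 6.6 forms the failure medians by treatment received for analyses that SAP 5.1 and 5.2 run as randomized. That mis-dispensed observed failures feed the other arm's median follows on any reading. That mis-dispensed subjects receive the other arm's median, and that never-dosed subjects have no defined value, follows only if the assignment clause also means actual treatment.

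The effect is probably small and depends on conduct. It is at most about 0.2 SE with 12 swapped subjects in each arm, all missing at Week 12, and with failure medians as far apart as the full planned effects. The counts and the gap are assumptions, since the documents supply neither. The primary result and every stated sample-size figure stand. This is a defect of specification in a supportive analysis and does not threaten the trial's conclusion.

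**What to change.** In Addendum 6.6, replace *using actual treatment* with *using randomized treatment*. State that this applies both to calculating the medians and to choosing the median assigned to each subject. Every ITT or ITTT subject with a missing Week 12 change then receives the randomized arm's median.

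The cost is one phrase in the addendum and one treatment variable in the program, settled before unblinding. There is one trade-off to accept knowingly: a subject randomized to active who never applied it will receive the median of active-arm failures. That follows from an as-randomized analysis and agrees with the main SAP's own wording of the rule.
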